6.2.3 Suspected unexpected serious adverse reactions (SUSARs)

Adverse reactions are all untoward and unintended responses to the food supplement or placebo related to any dose administered.

Unexpected adverse reactions are SUSARs if the following three conditions are met:

1. the event must be serious (see chapter 9.2.2);
2. there must be a certain degree of probability that the event is a harmful and an undesirable reaction to the medicinal product under investigation, regardless of the administered dose;
3. the adverse reaction must be unexpected, that is to say, the nature and severity of the adverse reaction are not in agreement with the product information as recorded in:
 - Summary of Product Characteristics (SPC) for an authorised medicinal product;
 - Investigator's Brochure for an unauthorised medicinal product.

The sponsor will report expedited the following SUSARs through the web portal *ToetsingOnline* to the METC:

- SUSARs that have arisen in the clinical trial that was assessed by the METC;
- SUSARs that have arisen in other clinical trials of the same sponsor and with the same medicinal product, and that could have consequences for the safety of the subjects involved in the clinical trial that was assessed by the METC.

The remaining SUSARs are recorded in an overview list (line-listing) that will be submitted once every half year to the METC. This line-listing provides an overview of all SUSARs from the study medicine, accompanied by a brief report highlighting the main points of concern.

The expedited reporting of SUSARs through the web portal Eudragilance or *ToetsingOnline* is sufficient as notification to the competent authority.

The sponsor will report expedited all SUSARs to the competent authorities in other Member States, according to the requirements of the Member States.

The expedited reporting will occur not later than 15 days after the sponsor has first knowledge of the adverse reactions. For fatal or life threatening cases the term will be maximal 7 days for a preliminary report with another 8 days for completion of the report.

6.3 Annual safety report

In addition to the expedited reporting of SUSARs, the sponsor will submit, once a year throughout the clinical trial, a safety report to the accredited METC, competent authority, and competent authorities of the concerned Member States.

This safety report consists of:

- a list of all suspected (unexpected or expected) serious adverse reactions, along with an aggregated summary table of all reported serious adverse reactions, ordered by organ system, per study;
- a report concerning the safety of the subjects, consisting of a complete safety analysis and an evaluation of the balance between the efficacy and the harmfulness of the medicine under investigation.

6.4 Follow-up of adverse events

There will be no follow-up of adverse events. There are no adverse events reported in previous use of Impryl. Therefore these are not expected. However, all SAEs and SUSARs will be followed until they have abated, or until a stable situation has been reached. Depending on the event, follow up may require additional tests or medical procedures as indicated, and/or referral to the general physician or a medical specialist. SAEs need to be reported till end of study within the Netherlands, as defined in the protocol

6.5 Data Safety Monitoring Board (DSMB) / Safety Committee

Due to the known safety of Impryl®, we do have the opinion that establishing a DSMB is not necessary.

7. STATISTICAL ANALYSIS

All data will be analyzed on an intention-to-treat basis. Data of patients who are lost to follow-up, will be included in their randomised group

will be included in their randomized group:

- Patients who are lost to follow-up during the treatment period are considered not to have achieved a pregnancy.
- Patients, who are lost to follow-up right after achieving a pregnancy of less than 8 weeks of gestation, are considered not to have achieved an ongoing pregnancy
- Patients, who are lost to follow-up right after achieving a pregnancy of 8 or more weeks of gestation, are considered to have achieved an ongoing pregnancy.

In addition, a per-protocol analysis will be performed for the primary outcome and the secondary outcomes overall pregnancy number, time to pregnancy, number of miscarriages and live birth rate.

Descriptive statistics will be calculated to check for major dissimilarities between study groups with respect to baseline information. Baseline data will be described quantitatively. For continuous variables, we will examine the distribution of the observations, and if normally distributed we will summarise them as means with standard deviations (SDs). If they are not normally distributed, then medians and inter-quartile ranges (IQRs) will be reported. For dichotomous data, we will provide counts and proportions.

The primary outcome variable 'ongoing pregnancy' will be assessed as follows. The ongoing pregnancy percentages as observed in the trial will be presented for both treatment arms, overall, and separately for the three strata (i.e. EM, IUI, IVF/ICSI). In order to adjust for possible imbalances between the treatment groups, the pregnancy percentages and differences in pregnancy percentages between the experimental and control group, and the corresponding 95% confidence intervals will be estimated using a fixed effects binomial model with an identity link, including intervention, fertility treatment, centre and female age (centered). If this model does not converge, a logit link will be used.

Time to ongoing pregnancy will be evaluated by the Kaplan-Meier approach; differences between the two arms will be tested with the log-rank test. Similar analyses will be conducted per stratum (EM, IUI or IVF/ICSI). The other secondary outcomes (overall pregnancy number, number of miscarriages, live birth rate, fertilization rate, embryo-utilization rate) will be evaluated similarly to the primary outcome. Changes in semen

analysis, leading to different fertility treatment categorisation, will be first calculated with descriptive statistics, with the following codes:

- 0: if there is no change in treatment category
- 1: if there is 1 category change (i.e. from IUI to EM), or -1 if it goes from less severe to severe (i.e. IUI to IVF)
- 2: if there are 2 category changes (i.e. from IVF to EM)

The changes will be summarized with descriptive statistics (mean, SD, median, range) and frequency tables per treatment and stratum. Further, the difference between the experimental and control group will be assessed with a fixed effects linear model, adjusted for centre and stratum.

Furthermore, adverse events will be summarized. Sensitivity analyses will be performed to evaluate possible effects in case of protocol amendments.

The per-protocol population will consist of all randomised patients without any major deviation from the protocol. A major protocol deviation is defined as

- Use of other nutritional supplements without a wash-out period
- Intake of study medication of less than 75% of the prescribed amount

Participants will be asked by automatic email to report in Castor their actual compliance to the intervention by taking note of total amount of consumed study medication (used boxes and tablets). Patients will also be asked to report about major changes of their lifestyle occurring during the study period (see page 22).

The results will be extracted from Castor. If there are missing data this will be mentioned along with the reason.

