SUMMARY

Rationale: Infertility is a worldwide problem and about 10%-15% of all couples will be affected by the inability to have children. In approximately 50% of infertile couples a male factor is involved. In the past decade, the role of oxidative stress on sperm has been researched thoroughly and found to be the problem in 30% to 80% of male infertility cases. Impryl® is a nutritional supplement which works on the metabolic system and regulation of oxidative stress by activating the 1-Carbon cycle and therefore recycling of homocysteine.

Objective: To determine the effectiveness of nutritional supplement Impryl® in men of infertile couples on ongoing pregnancy rate, with or without assisted reproduction technology (ART).

Study design: Multicentre, randomised double blind placebo controlled clinical trial/superiority study.

Study population: All participants in this study are male adults, age 18-50 years, part of a couple that is diagnosed with infertility, regardless the outcome of semen analysis. The couple will either start or is already started with fertility treatment, i.e. expectative management (EM, duration 6 months), intra-uterine insemination (IUI) with or without ovarian stimulation (mild ovarian hyperstimulation (MOH) or ovulation induction (OI)), either in vitro fertilization (IVF) or intracytoplasmic sperm injection (ICSI) treatment.

Intervention: Impryl® or placebo, with identical appearance one tablet each day for a total duration of maximal 6 months. Patients can start directly with fertility treatment and/or to conceive.

Main study parameters/endpoints: The primary outcome is the number of ongoing pregnancies confirmed by ultrasound at ≥ 10 -12 weeks, and conceived in the time window between randomization up to and including month 6 of intervention use. Secondary outcomes are change in semen parameters between baseline and 3 months intervention in IUI/IVF/ICSI group, based on (pre-wash) total motile sperm count (TMSC), leading to a different fertility treatment categorisation. Furthermore the number of pregnancies conceived in the optimal intervention time window, the overall number of pregnancies, time to pregnancy, embryo fertilization rate in IVF/ICSI, embryo-utilization rate in IVF/ICSI, number of miscarriages and live birth rate are documented within the study period of 15 months. The occurrence of adverse events will be reported.

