Number of pregnancies conceived in the optimal intervention time window, i.e. between start of month 4 till the end of month 6. Overall pregnancy rate. Time to pregnancy defined as both the time between a) randomization and reaching ongoing pregnancy, and as b) start of fertility treatment during the study (EM, IUI, IVF/ICSI) and reaching ongoing pregnancy. Change in semen parameters leading to different fertility treatment categorisation (for more details see page 26) between baseline and 3 months intervention, based on pre-wash total motile sperm count (TMSC) from the subpopulation from Radboudumc and sites that deliver a pre-wash TMSC before IUI/IVF/ICSI. Improvement between Impryl® and control group in fertilization rate and embryo-utilization rate in IVF/ICSI group. Fertilization rate is defined as the percentage of oocytes with 0 PN or ≥ 2 PN after insemination (IVF) or injection (ICSI). Abnormal fertilization such as 3PN will be recorded, in case this percentage differs or increases in the study group. The embryo-utilization rate (EUR) is defined as the number of high quality embryos obtained, embryo's used at transfer plus the number of embryos frozen, divided by the number of zygotes obtained in a cycle. Due to the differences in embryo evaluation and embryo selection criteria for cryopreservation, we decided to measure the relative increase in fertilization and utilization rate observed for each clinic.. Number of miscarriages defined as a non-vital intra-uterine pregnancy before 16 weeks of gestation. Live birth rate defined as beyond 24 weeks of gestation, the birth of a living child. Live births (beyond 24 weeks, defined as the birth of a living child) will be reported within follow-up time of 15 months. Furthermore the following adverse events will be reported: gastro-intestinal problems such as reflux, obstipation, diarrhea, nausea or vomiting, furthermore loss of appetite, headache, dizziness, pruritus or skin rash.

STUDY DESIGN

A multicentre randomised, double blind placebo controlled, clinical trial for Impryl® administration will be performed in the Department of Gynaecology and/or Reproductive Medicine in both academic and non-academic hospitals in The Netherlands.

The 16 centers participating in the study:

| Hospital | Principal investigator |
|---|--------------------------------|
| Radboudumc, Nijmegen | [name] |
| Slingeland Ziekenhuis, Doetinchem | [name] |

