1.3 Sample size calculation

The overall success rate (number of ongoing pregnancies, not specified per cycle number) in IVF and ICSI in the Netherlands was respectively 19.8% and 21.5% per cycle in 2015.(23) The cumulative number of ongoing pregnancies in IUI is estimated to be around 5 to 13% per cycle, around 18% after three cycles and 20-30% after six cycles. (24-26) Based on our Radboudumc data, the ongoing pregnancy rate in EM is estimated around 20% after 6 months.

A Cochrane review ‘antioxidants for male subfertility’ estimated the increase in clinical pregnancy rates after use of antioxidants with an Odds Ratio (OR) of 3.43 (95% CI 1.92 to 6.11, $P < 0.0001$, 7 RCTs, 522 men, $I^2 = 0\%$, low quality evidence). (27) However, this concerns low quality evidence, and the included population in this Cochrane review was couples with male factor subfertility, whereas in our study we also include couples with unexplained infertility. Therefore, we assumed a more conservative OR of 1.5. Assuming a 20% ongoing pregnancy rate in the placebo group, this reflects in an expected pregnancy rate of 27.3% in the Impryl® group

The study is designed as a superiority study. Based on the above mentioned data, we expect a 7.3% increase in ongoing pregnancy number when men are treated with Impryl® compared to placebo. However, after randomization patients can directly start with both intervention and achieving a pregnancy, either spontaneously or with fertility treatment. In these first months the effect of the intervention is expected to be suboptimal due to the duration of the spermatogenesis (72 days before whole renewal). Therefore we adjusted the expected increase of 7.3% to a more realistic effect of 6.5%. We assume an equal increase in all fertility groups (meaning EM, IUI and IVF/ICSI) from 20% to 26.5%.

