5.1.2 Secondary study parameters/endpoints

Number of pregnancies conceived in the optimal intervention time window, i.e. between start of month 4 till the end of month 6.

Overall number of pregnancies meaning the cumulative pregnancy number up to 9 months after start of intervention

Time to pregnancy defined as

- a) the time between start randomization and reaching ongoing pregnancy (confirmed by ultrasound)
- b) the time between start of fertility treatment during the study (EM, IUI, IVF/ICSI) and reaching ongoing pregnancy

Change in semen parameters in IUI/IVF/ICSI group based on pre-wash total motile sperm count (TMSC), leading to different fertility treatment categorisation (EM, IUI, IVF, ICSI), from a subpopulation of patients: Radboudumc patients and patients from other sites having pre-wash TMSC as standard procedure when semen is used for IUI or IVF/ICSI.

Improvement between Impryl® and control group in fertilization rate and embryo-utilization rate in IVF/ICSI group. Fertilization rate is defined as the percentage of oocytes with 0 PN or ≥ 2 PN after insemination (IVF) or injection (ICSI). Abnormal fertilization such as 3PN will be recorded, in case this percentage differs or increases in the study group. The embryo-utilization rate (EUR) is defined as the number of high quality embryos obtained, embryo's used at transfer plus the number of embryos frozen, divided by the number of zygotes obtained in a cycle. Due to the differences in embryo evaluation and embryo selection criteria for cryopreservation, we decided to measure the relative increase in fertilization and utilization rate observed for each clinic.

Number of miscarriages (defined as non-vital intra-uterine pregnancy before 16 weeks of gestation)

Live birth rate (beyond 24 weeks, defined as the birth of a living child) within study-period of 15 months

Adverse effects

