5.2 Randomisation, blinding and treatment allocation

RANDOMISATION AND TREATMENT ALLOCATION: All couples visiting a fertility specialist for the first time or for evaluation of fertility treatment will be informed on this study. Prior to or at their actual appointment they will receive the patient information (PIF). Randomisation will be performed, after signed informed consent has been obtained, using a web-based application (Castor). We will use permuted block-design, stratified for fertility treatment (1st) and recruiting centre (2nd). Block sizes are flexible. Participants will be randomised in a 1:1 ratio to study medication (Impryl®) or placebo. Assignment to medication, using the randomisation list, will either performed at the local centre or at Radboudumc by an independent person. This person is neither participating in clinical treatment nor processing the study data. Randomisation outcome is either A (Impryl®) or B (placebo).

CODING: coding starts immediately after informed consent has been obtained. In Castor each patient will receive a combination of one letter and 3 numbers. The code will be assigned as followed: Radboudumc (A), Slingeland (B), Canisius-Wilhelmina (C), Jeroen Bosch (D), Elisabeth-TweeSteden (E), Maasziekenhuis Pantein (F), Bernhoven (G), Maxima Medisch Centrum (H), Maastricht UMC+ (I), Gelre ziekenhuizen (J), Nij Geertgen (K) Rijnstate (L), Medisch Centrum Kinderwens (M), Nij Barrahûs (N),Fertiliteitscentrum Voorburg (O), Catharina Ziekenhuis Eindhoven (P) and Bravis Ziekenhuis (Q). For example, the first patient included in Radboudumc will receive the code A001. The code will not provide any information about the received intervention (Impryl® or placebo). The list of codes corresponding with patient information and received medication will be saved in an

separate file, locked (either digital with password or a locked cabinet), only accessible for the independent person who did the randomisation.

BLINDING: The study is double blinded. All personnel, the researchers and patients will remain blinded to the intervention being received, except the personnel performing randomisation and distributing the study medication.

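### The log-rank test for time to pregnancy is not tied to one of its two definitions, and the version starting at fertility treatment is not a clean intention-to-treat comparison

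*Combined protocol and SAP*

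**What the plan says.** The secondary objectives introduce the outcome with the words "Time to pregnancy defined as both the time between a) randomization and reaching ongoing pregnancy" and then add a version b). Section 5.1.2 repeats the pair and gives the second version as "the time between start of fertility treatment during the study (EM, IUI, IVF/ICSI) and reaching ongoing pregnancy". Neither place ranks them.

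Section 7 puts all data on an intention-to-treat basis. It plans Kaplan-Meier curves for time to ongoing pregnancy and states that "differences between the two arms will be tested with the log-rank test", with similar analyses in each fertility-treatment stratum. It refers to neither (a) nor (b), and it does not say that the overall test is stratified. Time to pregnancy is also repeated in the per-protocol analysis.

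Elsewhere, fertility treatment is treated as a design factor. It is the first randomisation stratum in section 5.2, and section 7 includes it in both the primary model and the semen-category model.

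Two further statements bear on version (b). On timing, the Summary says "Patients can start directly with fertility treatment and/or to conceive", and section 1.3 says "after randomization patients can directly start with both intervention and achieving a pregnancy, either spontaneously or with fertility treatment". On the effect itself, section 1.3 says "In these first months the effect of the intervention is expected to be suboptimal due to the duration of the spermatogenesis".

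**The concern.** Randomisation protects a comparison that starts at randomisation and keeps everyone. Version (b) does so only if treatment starts on the day of randomisation. Otherwise its clock starts later, and a couple reaches the start only by not conceiving first and by actually beginning treatment. If the supplement works during the wait, it changes who is left to be timed.

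The plan gives no rule for three kinds of couple:

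- IUI or IVF/ICSI couples who conceive naturally before treatment begins. Section 1.3 expects that spontaneous conception can occur.
- Couples who never start treatment.
- Couples already in treatment at entry, whom the Summary admits and section 1.2 allows up to a third cycle. Their start date during the study is not defined.

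At stake is the reading of one secondary outcome. The two versions can give different answers, nothing says which one is the result, and one of them can leave out or re-time couples because of something that happened after randomisation.

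**Working it through.** **The plan's own figure.** Inputs from section 1.3: 20% against 26.5%, 600 per arm, two-sided 5%. Power = Φ[(0.065·√600 − 1.96·√(2·0.2325·0.7675)) / √(0.2·0.8 + 0.265·0.735)] = Φ[(1.592 − 1.171)/0.596] = Φ(0.707) = 76.0%. This agrees with the stated 76%. No figure is given for time to pregnancy.

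**On the time scale.** With constant hazards, HR = ln(0.735)/ln(0.80) = 1.38. Expected events by 6 months are 600·0.20 + 600·0.265 = 279. Log-rank power from randomisation is Φ[(√279/2)·ln 1.38 − 1.96] = Φ(0.73), about 77%.

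**How many pregnancies could lack a (b) time.** The 1:3:2 ratio gives 200 EM, 600 IUI and 400 IVF/ICSI couples. EM is taken to start at once, so 1000 couples (500 per arm) could wait. The documents give neither waiting times nor natural conception rates for them. *Assume* a one-month wait for all 1000 and natural conception of 5%, 10% or 20% per 6 months (20% is the EM rate).

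At 20% with HR 1.38 throughout, the monthly hazard is −ln(0.80)/6 = 0.0372:

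- placebo: 500·(1 − e^(−0.0372)) = 18
- Impryl: 500·(1 − e^(−0.0372·1.38)) = 25
- share: 43/279, about 16% of pregnancies by 6 months

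The ranges below cover three effect shapes, each calibrated to 26.5% at 6 months: no lag (HR 1.38), half effect for 72 days (HR 1.24, then 1.47), and no effect for 72 days (HR 1.00, then 1.63). The 15-month column also assumes that the effect persists.

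| Natural conception per 6 months | No (b) time, 6 months | No (b) time, 15 months |
|---|---|---|
| 5% | 3–4% | 1–2% |
| 10% | 7–8% | 3–4% |
| 20% | 13–16% | 6–8% |

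With waits of 0.5 to 2 months the spans are 2–30% and 1–15%. With no wait the share is zero.

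**Direction.** In the 20% case the lost pregnancies split 25 Impryl to 18 placebo with no lag, 23 to 18 with the half effect, and 18 to 18 with the full lag. The simulated power of (b) minus that of (a) at 6 months follows, with the one-month wait, pre-treatment conceptions dropped and 2000 trials per scenario:

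| Effect shape | Power difference, (b) − (a) |
|---|---|
| No lag | −1 to −7 points |
| Half effect for 72 days | −1 to −3 points |
| No effect for 72 days | +2 to +5 points |

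At 15 months the two versions differ by about 1 point or less. The sign depends on the lag, which the plan expects but does not quantify.

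**Type I error.** With no treatment effect and waits of 1 or 2 months, both versions reject in 4.1–5.7% of 3000 simulated trials, which is compatible with 5%.

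**Stratifying the overall test.** Version (a), 6 months, HR 1.38, 4000 trials per row, both tests on the same data:

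| Placebo rate EM/IUI/IVF-ICSI | Unstratified | Stratified |
|---|---|---|
| 20/20/20% (the plan's assumption) | 76.7% | 76.6% |
| 20/18/21% | 74.9% | 75.1% |
| 20/25/21% | 81.3% | 81.5% |
| 20/30/21% | 84.7% | 85.0% |
| 15/15/30% (wider, assumed) | 75.7% | 76.9% |

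Rows two to four use rates found in or within the ranges of section 1.3. Both tests hold their level under no effect (4.8–5.2%).

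**The case against.** Both origins are stated where the endpoint is defined, and section 7 need not repeat them. The natural reading of the secondary objectives is that each version is tested, and the plan ranks none of its other secondary outcomes. This has weight: the origins are not missing. What is missing is the link from the test to a version, and a rule for couples with no (b) time.

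The waits may also be short. Inclusion is of couples starting treatment, some have already begun, and the Summary allows an immediate start. EM is itself listed as a treatment in version (b), so a waiting couple might be timed as EM. Giving all 1000 couples the EM conception rate is probably an upper bound. These points stand, so the percentages are illustrations and not estimates.

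A reader might infer that testing (b) produces false positives. The documents do not support that. The trial is double blind, so if the supplement does nothing, waits and early conceptions have the same distribution in both arms. The difficulty lies in interpreting (b) when there is an effect.

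A reader might also infer that the unstratified log-rank test is an error. It is not. It is valid, per-stratum analyses are planned, and under the plan's assumption of equal rates stratifying gains nothing.

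**Conclusion.** The point holds as a gap in specification for one secondary outcome. The log-rank test is not linked to (a) or (b), and a comparison of arms on (b) does not fit the intention-to-treat basis that section 7 sets for all data. The size and direction of the effect are unknown, and it vanishes if no couple waits. The ranges shown rest on assumed waits, assumed natural conception rates and the assumption that pre-treatment conceptions are dropped.

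It is tempting to conclude that (b) loses power or is biased against Impryl. The no-lag calculation points that way, but a full 72-day lag reverses the sign, so neither claim is made. The type I error of each version alone is sound. The primary outcome and the sample size are unaffected. Stratifying the overall test brings consistency with the randomisation and the primary model, with about 0 to 0.3 power points at rates from section 1.3.

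**What to change.** In section 7, before unblinding:

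- Name version (a), from randomisation, as the tested comparison, also for the per-protocol repeat.
- Use a log-rank test stratified by fertility treatment (EM, IUI, IVF/ICSI). Centre is not needed as a further stratum: 17 listed centres by 3 treatments is 51 cells of about 1200/51 ≈ 24 couples.
- Report version (b) descriptively, without an arm test. Give by arm the number of couples who conceived before treatment start and the number who never started. State which date counts as the start for couples already in treatment at entry.

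The cost is wording only, with no new visits and no change to other analyses. The one small downside is that (b), a declared secondary endpoint, loses its formal arm test.
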